##### *Statistical analysis*

The combinations peptide/radioactivity dose ranges (see Methodology).

Each of the 24 evaluable subjects is to receive two different  $^{68}\text{Ga}$ -OPS202 peptide/radioactivity dose range combinations. Hence, a total of 48 scans will be analysed (8 in each combination peptide/radioactivity dose range).

The number of scan sets generated will be as follows:

- All the 48 scans will serve for the primary and key secondary  $2 \times 3$  factorial analysis endpoints
- 24 sets for each of the two peptide mass dose ranges regardless of the radioactivity dose which will be analysed to describe the difference between these two dose ranges
- 16 sets for each radioactivity dose range regardless of peptide mass dose, which will be analysed to describe the differences between these three dose ranges.

The analysis will be descriptive and no formal statistical tests are planned for the primary and secondary endpoints. Mean, standard deviation, median and ranges will be estimated.

The primary endpoint and secondary tumour-to-background ratio and  $SUV_{max}$  endpoints' analyses will be performed following the  $2 \times 3$  factorial distribution of the imaging sets per combination of peptide/radioactivity dose ranges.

Overall differences among the three radioactivity doses, overall difference among the two peptide mass doses, and interaction between the peptide mass doses and radioactivity doses will be analysed.

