## 6 DIAGNOSTIC IMAGING OF SUBJECTS

### 6.1 Study Imaging Product

#### 6.1.1 Ga-OPS202

At Screening, subjects will be allocated a subject number. Following confirmation of eligibility for the study, subjects will be randomised to one of the following sequence of Ga-OPS202 peptide mass dose/ radioactivity dose ranges:

- Arm A: 5-20 µg/ 40-80 MBq at Visit 2 and 30-45 µg/ 100-140 MBq at Visit 3

or

- Arm B: 5-20 µg/ 100-140 MBq at Visit 2 and 30-45 µg/ 160-200 MBq at Visit 3

or

- Arm C: 5-20 µg/ 160-200 MBq at Visit 2 and 30-45 µg/ 40-80 MBq at Visit 3

Ga-OPS202 is a diagnostic medicinal product with three main components, namely:

- Ga, a positron emitter radionuclide with a half-life of 68 min
- NODAGA, a chemical chelator group, and
- JR11, an antagonist somatostatin analogue that binds to sst2 receptors

OPS202 (cold kit) is available for clinical trials in a 50 µg peptide dose vial, and is radiolabeled using a Ge/Ga-generator. Due to the short half-life (68 min) of the Ga radioisotope, on-site generation of Ga-labeled radiopharmaceuticals is mandatory. The Ga is eluted initially from the generator with hydrochloric acid and the eluate combined with the reconstituted peptide kit preparation. The radiolabelling occurs at room temperature. The product then undergoes radiopharmaceutical quality control (see Preparation, Radiolabeling and QC manual).

The radiolabelled OPS202 (Ga-OPS202) consists of 50 µg of peptide in a total volume of 6 mL (8.33 µg/mL). Sampling of 0.5 mL for QC yields 5.5 mL solution from which the volume to be administered is withdrawn. This volume to be injected is calculated to obtain the target peptide mass dose and the desired radioactivity dose.

The calculation of the volume takes into account the different components that determine the final radioactivity dose, the subject will be exposed to, in particular:

- The amount of Ga eluted from the generator which depends on the latter half-life
- The time elapsed between OPS202 (cold kit) radiolabelling and the injection of Ga-OPS202 to the subject (decay of Ga), the variation of which is a tool to adjust the final peptide/radioactivity dose required to be injected
- The required peptide mass dose and radioactivity dose of Ga-OPS202 to be injected.

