2.1.2 Per Protocol population (PP)

The Per Protocol (PP) population includes all randomised subjects for whom no major protocol violations/deviations impacting primary endpoint results occurred.

Any subject having a PET/CT scan which is non-evaluable/non-readable or having not meet the required minimum number of lesions by ICL readers and/or adjudicator will be considered impacting primary endpoint results, and therefore will be excluded from PP population. If there are disagreements between the readers, the adjudicator will have the final verdict if scans are evaluable or readable and how many number of lesions are seen.

Criteria for exclusion from the PP population will be provided in a separate Protocol Deviations Document (PDD) and Protocol Deviations Specifications.

Of note, if the screening visit duration is extended due to confirmation by ICL of eligibility regarding somatostatin receptor scan, this will not be considered a protocol deviation.

The Per Protocol criteria should be produced in advance of the database lock and generation of the PP population, and should be done using the first 50% of the subjects to avoid potential bias. In addition, a more extensive list of protocol deviations may be defined and reported in data listings.

Data will be excluded from the PP population on a subject basis and not on a visit basis. Of note, in case a subject performs only one of the two planned injections, he will be excluded from the PP population.

Reasons for subject exclusion from PP population will be presented in a summary table by dosing arm / sequence.

As specified in the study protocol section 3.3, replacement subjects of subjects CCI [REDACTED] will be recruited as soon as possible. In case subjects CCI [REDACTED] are found to be evaluable, corresponding replacement subjects will be excluded from PP population, regardless of the presence of major of protocol deviations (and provided CCI [REDACTED] have actually been replaced). Of note, correspondence between replacement subjects and their original subject will be obtained using the listing of randomised subjects from Medidata Balance (eCRF module for randomisation). This listing will be imported at the time of programming the statistical analysis.

As a results, PP population is expected to include 24 subjects: 8 subjects in each of the three study arms, who did not present with any major protocol deviation impacting PP and who were not replaced for any reason.

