3.2.1.1 Primary efficacy analysis

The primary endpoint is the relative lesion count, measuring the ratio of the number of lesions detected by ⁶⁸Ga-OPS202 to the number of lesions assessed by SOT.

The SOT is the CT scan images acquired at Visit 2 and Visit 3, using number of lesions identified by the reader on both timepoints together (provided by ICL), in order to take into account potential variability within subject or partial volume effect.

For each PET/CT assessment, this ratio will be computed, as indicated below:

$$\text{Relative lesion count} = \frac{\text{Number of lesions detected by } 68\text{Ga} - \text{OPS202}}{\text{Number of lesions detected by SOT}}$$

Numerator and denominator will be available in the database provided by ICL.

Selection of the optimal dose range for peptide mass and radioactivity of ⁶⁸Ga-OPS202 will be based on the observed highest relative lesion counts, based on provided descriptive statistics: n (number of non-missing observations), number of missing values (if any), arithmetic mean, standard deviation (SD), median and the range (minimum, maximum). Those descriptive statistics will be used for analysing all continuous parameters.

Analysis over all organs

For each PET/CT and PET assessment, relative lesion count will be computed over all lesions of all organs.

The denominator, based on SOT, will be computed over all organs.

Analysis per organ

For each PET/CT and PET assessment, relative lesion count will be computed for each of the following organs:

- Primary site of GEP-NET (among all subjects with at least one lesion detected by SOT on primary site of GEP-NET).
- Lymph nodes (among all subjects with at least one lesion detected by SOT on lymph nodes).
- Liver (among all assessed subjects with at least one lesion detected by SOT on liver).

- Axial/appendicular skeleton (bones) (among all assessed subjects with at least one lesion detected by SOT in bones).
- Lungs (among all assessed subjects with at least one lesion detected by SOT in lungs).

The denominator, based on SOT, will be computed for each organ.

Relative lesion count (over all organs then per organ) will be summarised using descriptive statistics for:

- each of the six combinations of injected peptide/radioactivity dose range, presented in such a way that study arms are explicit
- each of the two peptide mass dose ranges
- each of the three radioactivity dose ranges

No statistical test will be performed (no p-value nor confidence interval).

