Quality score will be analysed using descriptive statistics (frequencies and percentage), presented for:

- each of the six combinations of injected peptide/radioactivity dose range
- each of the two peptide mass dose ranges
- each of the three radioactivity dose ranges

Two sets of analysis will be performed for quality score:

- Based on assessment by reader A
- Based on assessment by reader B

Besides, readers scores will also be summed up together and presented for each of the six combinations of injected peptide/radioactivity dose range.

Individual values of quality score as well as which scan do reader prefer and reason for selecting scan 2 or 3 will be listed per reader, then by subject and by visit for both types of assessment (PET/CT and PET).

Other Secondary Endpoints:

b) Lesion SUV_{max}

For each PET assessment, lesion SUV_{max} (unit-less measure) will be measured for each lesion, up to a maximum of five most avid lesions per organ that are confirmed by SOT. In order to obtain a unique measure per organ, mean of the SUV_{max} will be computed within each of the four following organs:

- Liver
- Lymph nodes
- Bone
- Lungs.

Values will be available in the database provided by ICL.

Lesion SUV_{max} will be analysed using descriptive statistics, presented per organ and for:

- each of the six combinations of injected peptide/radioactivity dose range
- each of the two peptide mass dose ranges
- each of the three radioactivity dose ranges.

Individual values will be listed by subject, by organ and by visit.

- c) Absolute number of lesions detected by ^{68}Ga -OPS202, both as standalone and also compared to SOT

For each PET/CT and PET assessment, the number of lesions detected by ^{68}Ga -OPS202 and by SOT will be reported for each of the five following anatomic sites:

- Primary site of GEP-NET
- Lymph nodes
- Liver
- Axial/appendicular skeleton (Bones)
- Lungs

Values will be available in the database provided by ICL.

Absolute number of lesions detected by ^{68}Ga -OPS202 and difference with number of lesions detected by SOT will be analysed using descriptive statistics (for continuous variable), presented per anatomic site and for:

- each of the six combinations of injected peptide/radioactivity dose range
- each of the two peptide mass dose ranges
- each of the three radioactivity dose ranges

Also, for comparing lesions detection between ^{68}Ga -OPS202 and SOT, the following analyses will be performed:

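### Per-organ means by radioactivity range and by peptide range pool cells of unequal size, so part of one factor's effect can appear as an effect of the other

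*SAP*

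**What the plan says.** Protocol 6.1.1 gives three sequences. Arm A is "5-20 µg/ 40-80 MBq at Visit 2 and 30-45 µg/ 100-140 MBq at Visit 3", arm B is "5-20 µg/ 100-140 MBq at Visit 2 and 30-45 µg/ 160-200 MBq at Visit 3" and arm C is "5-20 µg/ 160-200 MBq at Visit 2 and 30-45 µg/ 40-80 MBq at Visit 3". Every low-peptide injection is at Visit 2 and every high-peptide injection at Visit 3, so peptide and visit cannot be separated.

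Over all organs the design is balanced. SAP 2.1.2 states that the "PP population is expected to include 24 subjects: 8 subjects in each of the three study arms", and the Protocol synopsis (Statistical analysis) counts "16 sets for each radioactivity dose range regardless of peptide mass dose".

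The per-organ rows of SAP 3.2.1.1 are restricted to subjects with an SOT lesion in the organ, for example "Axial/appendicular skeleton (bones) (among all assessed subjects with at least one lesion detected by SOT in bones". These rows are summarised for the six combinations, for each peptide range and for "each of the three radioactivity dose ranges", using n, arithmetic mean, SD, median and range. In SAP 3.2.1.2, tumour-to-background ratio and SUVmax use up to five lesions per organ that the SOT confirms. They get the same three levels of summary; SUVmax, for instance, is "presented per organ and for" each of them. No weighting or model is specified, and SAP 3.2.17 plans no covariate analysis.

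**The concern.** Each radioactivity range joins one low-peptide Visit 2 cell from one arm to one high-peptide Visit 3 cell from another. Each peptide range joins three radioactivity cells, one per arm. A raw mean over such a range is free of the other factor only when the arms are of equal size. The plan secures this over all organs, but the SOT restriction removes it within an organ.

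The synopsis intends to describe the overall radioactivity differences, the overall peptide difference and their interaction. SAP 3.2.1.1 bases selection of the optimal range on the highest relative lesion counts seen in the descriptive statistics, and SAP 3.2.1.2 adds the secondary and exploratory endpoints. With no test or confidence interval, readers will compare the means directly. A per-organ ranking of ranges could then partly reflect which arms happened to include subjects with disease in that organ.

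**Working it through.** **Plan's own figure.** With 8 subjects per arm and two scans each there are 8 scans per cell, 8 + 8 = 16 per radioactivity range, 3 × 8 = 24 per peptide range and 48 in total. This agrees with the synopsis.

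**Cell sizes per organ.** SAP 3.2.1.1 reads the SOT on both timepoints together, so for relative lesion count a subject enters or leaves both visits' cells as a pair. The sizes are nA, nB and nC. I use the same sizes as an approximation for tumour-to-background ratio and SUVmax.

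**Leak into radioactivity means.** Let d be the high-minus-low peptide difference, including any visit effect. The share of high-peptide scans in each range is:

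- 40-80 MBq (A at Visit 2, C at Visit 3): nC/(nA+nC)
- 100-140 MBq (B at Visit 2, A at Visit 3): nA/(nA+nB)
- 160-200 MBq (C at Visit 2, B at Visit 3): nB/(nB+nC)

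The false difference between two ranges is d times the difference in their shares. At 8/8/8 all shares are 0.50 and nothing leaks. For arm sizes from 1 to 8, the three shares are equal only when nA = nB = nC.

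Example: arms 5/3/2, no radioactivity effect, low 0.70, high 0.80 (d = 0.10).

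- 40-80: (5×0.70 + 2×0.80)/7 = 0.729
- 100-140: (3×0.70 + 5×0.80)/8 = 0.7625
- 160-200: (2×0.70 + 3×0.80)/5 = 0.760

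The largest false gap is 0.034, or 0.34d. Averaging the two cell means gives 0.75 in every range. With milder imbalance, 7/6/5, the shares are 5/12 = 0.417, 7/13 = 0.538 and 6/11 = 0.545, a gap of 0.13d.

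**Leak into peptide means.** Suppose there is no peptide or visit effect, and 40-80 MBq is lower than the other two ranges by e. With N = nA+nB+nC, the share of 40-80 scans is nA/N in the low-peptide mean and nC/N in the high-peptide mean. The false peptide difference is e(nA−nC)/N.

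Example: arms 5/3/2, 0.70 at 40-80 and 0.80 elsewhere (e = 0.10).

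- Low peptide: (5×0.70 + 3×0.80 + 2×0.80)/10 = 0.75
- High peptide: (5×0.80 + 3×0.80 + 2×0.70)/10 = 0.78

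The false gap is 0.03, or 0.3e. Averaging the three cell means gives (0.70+0.80+0.80)/3 = 0.767 for both. With 7/6/5 the gap is (7−5)/18 = 0.11e.

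**How often and how much.** The documents give no per-organ numbers. I therefore took nA, nB and nC as independent Binomial(8, p) and enumerated all cases exactly. Gaps are the largest difference in high-peptide share among the three radioactivity ranges, in units of d, given that every range has at least one scan.

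| Assumed p | Arms unequal | Mean gap | Median gap | 90th percentile |
|---|---|---|---|---|
| 0.90 | 86% | 0.09 | 0.07 | 0.14 |
| 0.75 | 94% | 0.16 | 0.13 | 0.27 |
| 0.58 (7/12) | 95.5% | 0.23 | 0.20 | 0.42 |
| 0.30 | 95% | 0.45 | 0.42 | 1.00 |
| 0.20 | 93% | 0.59 | 0.50 | 1.00 |

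The value 0.75 is 9/12, from the nine subjects with malignant liver lesions among 12 in the earlier study (Protocol 1.1). It is only a guide, because those were receptor and OPS202 scans, not CT. A gap of 1.00 arises when an arm is empty: one range mean is then wholly low-peptide and another wholly high-peptide.

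**The case against.** Several points against the concern stand.

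- The first summary in SAP 3.2.1.1, overall and per organ, is by the six combinations with arms made explicit, and it includes n and the mean. Individual values are also listed by arm, subject and visit. A careful reader can see the imbalance and compute the equally weighted mean. The table shells in Appendix 2 are not available, so it cannot be judged whether cell sizes will stand beside the range means.
- The analysis is descriptive, and no rule selects a dose from a per-organ range mean. Selection draws on all endpoints together.
- The sponsor expects peptide mass in this range not to affect detection (Protocol 1.5) and expects no change in lesion counts from progression between visits (Protocol 7). If d is zero, nothing leaks into the radioactivity means.
- The proportion of cases with unequal arms includes trivial imbalance such as 8/8/7.

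These points limit the consequence but do not remove the defect. Peptide mass is one of the two factors in the primary objective, so the summary should not need d to be zero. Protocol 7 also allows for technical variation between the two scans, which d would include. The mirror leak is the more plausible one, because the synopsis and Protocol 1.5 anticipate poorer signal at 40-80 MBq.

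A reader might infer that the primary all-organ comparison is affected too. The documents do not support that: at 8/8/8 the shares are equal, replacement subjects are meant to preserve that balance, and the count of 16 sets per range describes this balanced set. Nor does the point reach absolute lesion counts (SAP 3.2.1.2 c) or the quality score. Neither is restricted to subjects with an SOT lesion in the organ, so their cells stay equal while the PP set is 8/8/8.

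**Conclusion.** The point holds for per-organ relative lesion count, tumour-to-background ratio and SUVmax. For these, raw pooled means by radioactivity range can carry part of the peptide and visit effect, and raw pooled means by peptide range can carry part of the radioactivity effect. Unequal arms are very likely in any one organ (86% to 95.5% in the table) but are not a stated fact.

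The leak is a fraction of the other factor's effect. For the radioactivity means its median is about 0.13d at 75% prevalence and 0.42d to 0.50d at 30% to 20%. It is zero if the effect is zero or the arms are equal. The prevalences, d and e are assumptions; the documents give none of them. The binomial model also assumes independent arms of 8.

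It would be too strong to say that the plan will select the wrong range. No selection rule rests on these margins, and the six-cell table is reported alongside them. This is a worthwhile correction to subsidiary rows that feed an overall judgement.

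**What to change.** In SAP 3.2.1.1 (per-organ analysis) and SAP 3.2.1.2 a) tumour-to-background ratio and b) SUVmax:

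- Define each radioactivity-range mean as the unweighted average of its two cell means, and each peptide-range mean as the unweighted average of its three cell means.
- Print the cell sizes beside each range mean.
- Show no range mean when a contributing cell is empty.
- Keep the raw pooled n, median and range as description only.

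Apply the same rule to the all-organ row if the final PP set is not 8/8/8. Leave absolute lesion counts and the quality score as planned while the PP set is 8/8/8.

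The cost is SAP wording and one derived line per table, with no new data. A range mean loses precision when one of its cells holds only one or two subjects. Equal weighting also does not remove differences between the subjects of different arms, which still enter the radioactivity contrasts because each range draws on a different pair of arms.

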3.2.1.2 Secondary efficacy analysis

All secondary and exploratory analyses will be performed on PP population only.

Selection of the optimal dose range for peptide mass and radioactivity of ^{68}Ga -OPS202 will be based on the provided descriptive statistics for all secondary and exploratory efficacy endpoints, in addition to primary endpoint.

Key Secondary Endpoint:

a) Image quality

Quantitative measure:

For each PET assessment, image quality will be quantitatively measured by the tumour-to-background ratio, which will be obtained using the mean of all lesions tumour-to-backgrounds, for each of the four following organs:

- Liver
- Lymph nodes
- Bone
- Lungs

For up to five most avid lesions per organ that are confirmed by SOT, the tumour-to-background ratio will be computed as lesion SUV_{mean} divided by the SUV_{mean} of the subject's reference tissue (tumour-free liver or aortic blood).

Tumour-to-background ratio is a unit-less measure. A high tumour-to-background ratio indicates high effectiveness of ^{68}Ga -OPS202 as a diagnostic agent.

Tumour-to-background ratio will be analysed using descriptive statistics, presented for each of the four organs and for:

- each of the six combinations of injected peptide/radioactivity dose range
- each of the two peptide mass dose ranges
- each of the three radioactivity dose ranges

Individual values of tumour-to-background ratio will be listed by subject, by organ and by visit. Background location will be specified (L: Liver, B = Aortic blood).

Qualitative measure:

A qualitative analysis of the image assessed by the independent blinded readers will be performed to back up the quantitative quality measured by tumour-to-background analysis. This qualitative assessment will be performed using a quality score.

For each PET/CT and PET assessment, each independent blinded reader will perform a direct comparison of the two ^{68}Ga -OPS202 scans (Visit 2 and Visit 3, that have with different peptide and radioactivity doses). He/she will note which of the pair provides superior images based on overall image quality and lesion count, attributing a score for each assessment.

The score for the assessment having superior images will be set to “1”, and score for the assessment not selected will be set to “0”. In case of equal quality, both assessments will have a score of “1”.

Values will be available in the database provided by ICL.

Quality score will be analysed using descriptive statistics (frequencies and percentage), presented for:

- each of the six combinations of injected peptide/radioactivity dose range
- each of the two peptide mass dose ranges
- each of the three radioactivity dose ranges

Two sets of analysis will be performed for quality score:

- Based on assessment by reader A
- Based on assessment by reader B

Besides, readers scores will also be summed up together and presented for each of the six combinations of injected peptide/radioactivity dose range.

Individual values of quality score as well as which scan do reader prefer and reason for selecting scan 2 or 3 will be listed per reader, then by subject and by visit for both types of assessment (PET/CT and PET).

Other Secondary Endpoints:

b) Lesion SUV_{max}

For each PET assessment, lesion SUV_{max} (unit-less measure) will be measured for each lesion, up to a maximum of five most avid lesions per organ that are confirmed by SOT. In order to obtain a unique measure per organ, mean of the SUV_{max} will be computed within each of the four following organs:

- Liver
- Lymph nodes
- Bone
- Lungs.

Values will be available in the database provided by ICL.

Lesion SUV_{max} will be analysed using descriptive statistics, presented per organ and for:

- each of the six combinations of injected peptide/radioactivity dose range
- each of the two peptide mass dose ranges
- each of the three radioactivity dose ranges.

Individual values will be listed by subject, by organ and by visit.

- c) Absolute number of lesions detected by ^{68}Ga -OPS202, both as standalone and also compared to SOT

For each PET/CT and PET assessment, the number of lesions detected by ^{68}Ga -OPS202 and by SOT will be reported for each of the five following anatomic sites:

- Primary site of GEP-NET
- Lymph nodes
- Liver
- Axial/appendicular skeleton (Bones)
- Lungs

Values will be available in the database provided by ICL.

Absolute number of lesions detected by ^{68}Ga -OPS202 and difference with number of lesions detected by SOT will be analysed using descriptive statistics (for continuous variable), presented per anatomic site and for:

- each of the six combinations of injected peptide/radioactivity dose range
- each of the two peptide mass dose ranges
- each of the three radioactivity dose ranges

Also, for comparing lesions detection between ^{68}Ga -OPS202 and SOT, the following analyses will be performed:

- Number of subjects having lesions detected by ^{68}Ga -OPS202 when no lesions is detected by SOT (so called “False Positive” lesions, although in this instance, without histology, this determination is equivocal), in each of five anatomic sites (Primary site of GEP-NET, Lymph nodes, Liver, Axial/appendicular skeleton (Bones), Lungs).
- Number of subjects having lesions detected by SOT when no lesions is detected by ^{68}Ga -OPS202 (so called “False negative” lesions, although in this instance, without histology, this determination is equivocal), in each of five anatomic sites (Primary site of GEP-NET, Lymph nodes, Liver, Axial/appendicular skeleton (Bones), Lungs).

Individual values of number of lesions detected by ^{68}Ga -OPS202 and difference with number of lesions detected by SOT will be listed by subject, by anatomic site and by visit for both types of assessment (PET/CT and PET),

- d) The primary and secondary endpoints will also be evaluated on a radioactivity dose/kg of body weight.

For each subject's visit, the radioactivity dose/kg (in MBq/kg) will be computed using following formula:

$$\text{Radioactivity dose/kg} = \frac{\text{Injected radioactivity dose at visit (MBq)}}{\text{Patient's weight at visit (kg)} *}$$

*In case subject's weight is not available at visit, last weight value will be used.

First, as a preliminary step, a boxplot will be drawn in order to describe subjects' weight at Visit 2, for each of 6 combinations of injected peptide/radioactivity dose range.

The following efficacy criteria will be analysed:

- Primary criterion: Relative lesion count (overall and per each of the five anatomic sites)
- Secondary criteria: Image quality (tumour-to-background ratio for each of the four organs, quality score), lesion SUV_{max} in each of the four organs, absolute number of lesions in each of the five anatomic sites, difference between number of lesions detected by ⁶⁸Ga-OPS202 and number of lesions detected by SOT.

As graphical analysis of the radioactivity dose/kg, the following plots will be performed (plot of individual values) with both peptide dose ranges shown by using two different symbols:

- Scatterplot of radioactivity dose/kg x relative lesion count, per organ and overall
- Scatterplot of radioactivity dose/kg x tumour-to-background ratio, for each of the four organs (Lymph nodes, Liver, Axial/appendicular skeleton (Bones), Lungs)
- Scatterplot of radioactivity dose/kg x quality score
- Scatterplot of radioactivity dose/kg x SUV_{max}, per each of the four organs
- Scatterplot of radioactivity dose/kg x absolute number of lesions detected by ⁶⁸Ga-OPS202, per each of the five anatomic sites (Primary site of GEP-NET, Lymph nodes, Liver, Axial/appendicular skeleton (Bones), Lungs).
- Scatterplot of radioactivity dose/kg x difference between number of lesions detected by ⁶⁸Ga-OPS202 and number of lesion detected by SOT, per each of the five anatomic sites.

Besides, as categorical analysis of the radioactivity dose/kg, the following ranges will be used for the analysis, based on the observed distribution of the continuous radioactivity dose/kg among PP population:

- [min-Q1] MBq/kg
-]Q1-median] MBq/kg
-]median-Q3] MBq/kg
-]Q3-max] MBq/kg

Based on those ranges, summary tables with descriptive statistics for each of the four ranges of radioactivity dose/kg will be provided. Also, into each of the four ranges of radioactivity dose/kg, the two peptide doses will be analysed, that will lead to analyse, with same methodology as previously, 8 combinations of radioactivity dose/kg x peptide mass dose ranges.

Listings of individual values will be provided by ascending radioactivity dose/kg range then by ascending radioactivity dose/kg, and by subject (and by organ when applicable).

Exploratory efficacy endpoints:

- e) Preliminary diagnostic sensitivity of ⁶⁸Ga-OPS202 imaging of GEP-NETs by both subject-based and lesion-based analysis compared to standard-of-truth; and organ-based specificity, by radioactivity dose range (i.e. 40-80 MBq, 100-140 MBq, 160-200 MBq, 100-200 MBq, 40-200 MBq).

Diagnostic sensitivity between ⁶⁸Ga-OPS202 and SOT will be assessed using performance specified in table below.

Table 3 Diagnostic performance of ⁶⁸Ga-OPS202 compared to SOT

⁶⁸ Ga-OPS202 PET/CT scan results	SOT results	
	# of lesions detected	# of lesions not detected
# of lesions detected	True Positive (TP)	False Positive (FP)
# of lesions not detected	False Negative (FN)	True Negative (TN)

The sensitivity corresponds to the probability that the ⁶⁸Ga-OPS202 imaging detects the lesions, given that the lesions are positive in SOT.

For each PET/CT assessment, the sensitivity will be computed using following formula, per each of the organs (lesion-based approach) and overall (subject-based approach):

$$Sensitivity = \frac{TP}{TP + FN}$$

For lesion-based approach (per organ), following organs will be analysed: Primary site of GEP-NET, Lymph nodes, Liver, Axial/appendicular skeleton, Lungs. In case no lesions were detected by the SOT, sensitivity cannot be computed due to null denominator. Therefore only organs with lesions detected by SoT will be analysed for sensitivity.

To allow for computation of sensitivity, detected lesions will be counted from the “Lesion Matching Table” provided by ICL.

Additionally, an organ-based specificity analysis will be performed, based on PET/CT assessments.

For each organ:

- If there are 0 lesions detected in an organ on both ^{68}Ga -OPS202 scan and SOT, it will be counted as TN.
- If there is at least 1 lesion detected in an organ on ^{68}Ga -OPS202 scan but not on SOT, it will be counted as FP.

Example for a given subject, a given visit VX:

	At least one lesion detected by ^{68}Ga -OPS202 at Visit VX	At least one lesion detected by SOT	Type of lesion for analysis
Primary site of GEP-NET	No	Yes	FN
Lymph nodes	Yes	No	FP
Liver	Yes	Yes	TP
Bones	No	No	TN
Lungs	Yes	Yes	TP

Specificity will be calculated using the following formula:

$$\text{Specificity} = \frac{TN}{TN + FP}$$

In the example above, ^{68}Ga -OPS202 PET/CT assessment will have a specificity equal to 0.5 when compared to SOT.

Subject-based and lesion-based sensitivity along with organ-based specificity will be summarised using descriptive statistics for:

- each of the six combinations of injected peptide/radioactivity dose range
- each of the two peptide mass dose ranges
- each of the three radioactivity dose ranges

It will be also summarised using descriptive statistics for following five radioactivity dose groups:

- ^{68}Ga -OPS202 PET/CT at 40 to 80 MBq
- ^{68}Ga -OPS202 PET/CT at 100 to 140 MBq
- ^{68}Ga -OPS202 PET/CT at 160 to 200 MBq
- ^{68}Ga -OPS202 PET/CT at 100 to 200 MBq *
- ^{68}Ga -OPS202 PET/CT at 40 to 200 MBq *

Note: *A subjects' scan will use either his visit 2 or visit 3 scan, and not both. ^{68}Ga -OPS202 PET/CT at (100-200 MBq) and (40-200 MBq) will use the same subjects except the scan/visit with the lowest dose will be read. i.e.

- For 100-200 MBq, will choose Arm: A visit3, B visit2, C visit 2
- For 40-200 MBq, will choose Arm: A visit2, B visit2, C visit 3

Individual values of subject-based, lesion-based sensitivity and organ-based specificity will be listed by subject and by visit for this assessment (PET/CT).

f) Comparison to sstr2 agonist positive scan results will be computed for sensitivity analysis. In order to compare ^{68}Ga -OPS202 PET/CT to sstr2 agonist PET assessments, the two following analyses will be performed:

- Sensitivity and specificity of previously acquired sstr2 agonist PET versus SOT. Diagnostic sensitivity of previously acquired sstr2 agonist scan (at Visit 1) will be analysed by subject-based analysis and lesion-based approaches (per organ) compared to SOT.

Also, organ-based specificity will be computed.

Methodology for computing sensitivities and specificity will be same as described in e), with sstr2 PET instead of ^{68}Ga -OPS202 PET/CT assessments, compared to SOT.

As sstr2 agonist PET scan is performed only at Visit 1 and as SOT is not specific to V2 or V3, values of sensitivities/specificity will be unique per subject.

Subject-based and lesion-based sensitivity along with organ-based specificity will be summarised using descriptive statistics for all subjects.

Individual values of subject-based, lesion-based sensitivity and organ-based specificity will be listed by subject for this assessment (sstr2 PET).

- Comparison of sensitivity of ^{68}Ga -OPS202 PET/CT to previously acquired SSTR2 agonist PET.

The subject-based sensitivity of ^{68}Ga -OPS202 PET/CT will be compared to sensitivity of previously acquired SSTR2 agonist PET, both assessed vs SOT.

Therefore for each subject*visit, the difference will be computed as:

Sensitivity (PET/CT vs SOT) – Sensitivity (SSTR2 vs SOT).

Note that value of subject-based sensitivity (SSTR2 vs SOT) will be unique per subject.

This difference will be summarised using descriptive statistics for:

- each of the six combinations of injected peptide/radioactivity dose range
- each of the two peptide mass dose ranges
- each of the three radioactivity dose ranges

It will be also summarised using descriptive statistics for following five radioactivity dose groups:

- Difference of ^{68}Ga -OPS202 PET/CT (at 40 to 80 MBq) to SSTR2 PET
- Difference of ^{68}Ga -OPS202 PET/CT (at 100 to 140 MBq) to SSTR2 PET
- Difference of ^{68}Ga -OPS202 PET/CT (at 160 to 200 MBq) to SSTR2 PET
- Difference of ^{68}Ga -OPS202 PET/CT (at 100 to 200 MBq) to SSTR2 PET
- Difference of ^{68}Ga -OPS202 PET/CT (at 40 to 200 MBq) to SSTR2 PET

g) SUV_{max} ratio for lesions

For each PET assessment, lesion SUV_{max} will be measured for each of the most avid lesions identified per organ (up to a maximum of five most avid lesions per organ that are confirmed by SOT) and reported in the ICL database.

For each organ, the SUV_{max} ratio will be computed as follows:

$$SUV_{max} \text{ ratio} = \frac{SUV_{max}}{SUV_{mean} \text{ of the subject's reference tissue (tumour – free liver)}}.$$

It will be analysed using descriptive statistics, presented for:

- each of the six combinations of injected peptide/radioactivity dose range
- each of the two peptide mass dose ranges
- each of the three radioactivity dose ranges

Individual values of SUV_{max} ratio will be listed by subject, by organ and by visit.

Background location will be specified (L: Liver, B = Aortic blood).

h) SNR in the liver

SNR will be calculated from lesion-free VOI (reference tissue) using following formula:

$$SNR = \frac{SUV_{mean}}{SUV_{SD}}$$

Those SUV_{mean} and SUV_{SD} will be available in the database provided by ICL.

A higher SNR in the liver indicates higher effectiveness of ^{68}Ga -OPS202 as a diagnostic agent.

It will be analysed using descriptive statistics, presented for:

- each of the six combinations of injected peptide/radioactivity dose range
- each of the two peptide mass dose ranges
- each of the three radioactivity dose ranges

Individual values of SNR in the liver will be listed by subject and by visit.

Background location will be specified (L: Liver, B = Aortic blood).

Additional listing:

A listing of SUV measurements by lesion and per organ will be provided, including following data listed by subject and by visit:

- Lesion SUV_{mean}
- Lesion SUV_{max}
- Lesion SUV_{max} ratio
- Lesion Tumour-to-background ratio

3.2.2 *Safety*

All safety data will be included in the data listings and summary tables will be based on the Safety population and presented by combination of injected peptide/radioactivity dose range and overall.

AEs will be allocated to each combination of injected peptide/radioactivity dose range following the following rule: AEs will be allocated to the last dose of ^{68}Ga -OPS202 received, based on AE start date/time.

Same rule will be applied for analysing concomitant medications, based on treatment start date/time.

For the safety parameters measured at each visit (ECG, laboratory data, vital signs, physical examinations), allocation to each combination of injected peptide/radioactivity dose range will follow the rule below:

- A unique baseline value will be defined per subject, as the last measurement collected prior to the first IIP administration
- For the post-baseline visits, assessments will be allocated to the last dose of ^{68}Ga -OPS202 received, based on date/time of assessment.

